7.5.2 Other Assessments

7.5.2.1 Risk markers

The following risk markers will be recorded/measured at the following time points:

- 8-epi-PGF2 α to be measured in 24-hour urine on Day 0 and Day 5.
- 11-DTX-B2 to be measured in 24-hour urine on Day 0 and Day 5.

7.5.2.2 CYP1A2 Activity test

Cytochrome P450 1A2 activity will be measured at Day 0 and at Day 5. Measurement of enzyme activity will be assessed through PX and CAF plasma molar concentrations approximately 6 hours (± 15 minutes) after the intake of a cup of coffee made from 4.2 g ($\pm 10\%$) regular instant coffee (Nescafé Gold Instant; Nestlé; Deutschland; CAF content: 72 mg/2 g) with 150 ml ± 10 ml water. The CAF content will be approximately 150 mg CAF (Faber and Fuhr, 2004). The exact time of the intake of the cup of coffee in the morning and of the blood sampling (taken 6 hours [± 15 minutes] after the intake of the coffee) must be recorded. Cytochrome P450 1A2 activity will be assessed by the measurement of the molar PX/CAF metabolic ratio (Faber and Fuhr, 2004).

7.5.2.3 CYP2A6 activity

Cytochrome P450 2A6 activity will be measured in plasma on Day 0, and on Day 6, using the molar metabolic ratio of *trans*-3'-hydroxycotinine/cotinine (Jacob et al, 2011). Blood sampling for CYP2A6 activity must be done prior to product use.

Cytochrome P450 2A6 activity drives the hepatic metabolism of nicotine to cotinine and subsequent metabolites.

7.5.2.4 Ames Mutagenicity Test

Urine mutagenicity, a biomarker for measuring mutagen load, will be measured on Day 0 and on Day 5 in 24-hour urine.

The urinary determination of each sample will be done in one bacterial strain (*S. typhimurium* strain YG1024), using S9 metabolic activation and 4 doses for each of the urine extracts.

7.6 Laboratory Assessments

7.6.1 Clinical Chemistry, Hematology, and Urine Analysis for Safety panel

Hematology, clinical chemistry, and urine analysis for the safety panel will be measured at Screening, Day 0, and at Day 6. Blood samples will be taken after at least 8 hours of fasting (see Section 6.6.2). The urine test will be performed semi-quantitatively as a urine dip-stick test. Parameters to be measured are listed in Table 3.

**Table 3. Clinical Laboratory Parameters for Safety Panel**

| Hematology | Clinical Chemistry | Urine analysis |
|--|------------------------------------|-------------------------|
| - Hematocrit (Hct) | - Albumin | - pH |
| - Hemoglobin (Hb) | - Total protein | - Bilirubin |
| - Mean corpuscular hemoglobin (MCH) | - Alkaline phosphatase (AP) | - Glucose |
| - Mean corpuscular hemoglobin concentration (MCHC) | - Alanine aminotransferase (ALT) | - Nitrite |
| - Mean corpuscular volume (MCV) | - Aspartate aminotransferase (AST) | - Red blood cell traces |
| - Platelet count | - Blood urea nitrogen (BUN) | - Protein |
| - Red blood cell (RBC) count | - Creatinine | - Specific gravity |
| - White blood cell (WBC) count | - Gamma-glutamyl transferase (GGT) | |
| - Differential WBC count: | - Fasting Glucose | |
| • Neutrophils | - Lactate dehydrogenase (LDH) | |
| • Basophils | - Potassium | |
| • Eosinophils | - Sodium | |
| • Lymphocytes | - Total bilirubin | |
| • Monocytes | - Direct bilirubin | |
| | - Total cholesterol | |
| | - Triglycerides | |

7.6.2 Serology

A test for HbsAg, HCV, and anti-HIV1/2 and p24 antigen will be done at Screening. In case of positive results, the subject will be referred to appropriate medical care.

7.6.3 Urine Drug Screen

A urine drug screen will be performed at the study site at the Screening Visit and on the Day of Admission (Day -2). The urine will be screened for amphetamines, barbiturates, benzodiazepines, cannabinoids, cocaine, and opiates.

Confidentiality statement: Data and information contained in this document are considered to constitute trade secrets and confidential commercial information, and the legal protections provided to such trade secrets and confidential information are hereby claimed under the applicable provisions of applicable law. No part of this document may be publicly disclosed without the written consent of Philip Morris Products S.A.

7.6.4 Urine Cotinine Screening

A urine dip-stick cotinine test will be performed at Screening and at Admission (Day -2) in order to confirm the subject's smoking status. The test must detect cotinine with a cotinine threshold of ≥ 200 ng/ml (i.e., One-Step Cotinine Test 008A086, Ultimed, Belgium).

7.6.5 Alcohol Breath Test

Subjects will have a breath alcohol test at the Screening Visit and at Admission (Day -2) using an alcometer device (e.g., Alcotest 7410 Plus, Dräger).

7.6.6 Urine Pregnancy Testing

All female subjects will undergo pregnancy testing at the Screening Visit, at Admission (Day -2), at Day 6. Female subjects with a positive pregnancy test at the Screening Visit or at Day -2 cannot be enrolled and will be considered a screening failure. The product test at Admission must be done only in female subjects with a negative urine pregnancy test. In any case of a positive urine pregnancy test, the Investigator or designee will inform the subject about the risks associated with smoking during pregnancy. In the event of an unclear urine pregnancy test, absence of pregnancy should be confirmed by a serum follicle stimulating hormone level >20 IU/l.

All pregnancies detected during the study must be reported and handled as described in Section 8.5.

7.7 Sample Handling and Storage

All blood samples are to be tested at a central laboratory with the exception of COHb blood sample and the safety laboratory panel which will be tested at a local laboratory (see Appendix 2). The urine dip-stick for the safety laboratory, urine pregnancy tests, urine drug screen, and urine cotinine tests will be done by personnel at the study sites.

Detailed procedures for sample collection and handling of samples will be described in a separate Sample Handling Manual (SHM). Safety laboratory samples will be destroyed as per the laboratory's standard procedures. All other samples (except bio-banking samples) will be destroyed after the Clinical Study Report (CSR) has been finalized. The facility/ies at which the samples are stored will be informed in writing by the Sponsor when destruction of the samples will be allowed.

The bioanalytical lab(s) are listed in Appendix 2.

7.7.1 Blood Samples

Blood samples will be collected by qualified and trained site personnel. Subjects should be in a seated position during blood collection. The maximal total volume of blood drawn for each subject will be around 170 ml, which includes 20 ml for safety and repeated analysis, 20 ml of blood for long-term storage of the biobanking samples for further analysis of biomarkers

Confidentiality statement: Data and information contained in this document are considered to constitute trade secrets and confidential commercial information, and the legal protections provided to such trade secrets and confidential information are hereby claimed under the applicable provisions of applicable law. No part of this document may be publicly disclosed without the written consent of Philip Morris Products S.A.

of exposure and risk markers (only if additional consents are given, see Section 7.7.3), and 10 ml for long-term storage biobanking samples for further transcriptomics analysis (only if additional consents are given, see Section 7.7.3).

The blood sampling for transcriptomics and the data related to these samples will be anonymized. Anonymised data and samples are initially single or double coded where the link between the subjects' identifiers and the unique code(s) is subsequently deleted. This is applicable for the blood bio-banking for transcriptomics only.

7.7.2 Urine Samples

Spot urine samples will be used for the urine drug screen, urine cotinine screen, urine pregnancy tests, and safety urinalysis.

For the 24-hour urine collection, subjects will empty their bladders shortly before 06:30 AM on the study day indicated in the Schedule of Events (Appendix 1). The collection period starts at 06:30 AM and ends on the following day at 06:29 AM. Shortly before 06:29 AM, after nearly 24-hours of urine collection, subjects will empty their bladder again and this urine will be used as the final portion of the 24-hour urine sample. During the sampling period, all urine passed must be collected and put into the sampling bottle, with the exception of about 10 ml for the spot urine tests (described above). No urine must be passed into the toilet. The start and the end time of the 24-hour urine collection will be recorded by the study site staff.

For assessment of urine BoExp, creatinine for normalization of urine BoExp, sample bio-banking and urine mutagenicity, aliquots from the 24-hour urine collection will be taken. In the Schedule of Events for the 24-hour urine collection (see Appendix 1) the dot corresponds to the day on which the 24-hour urine collection period starts. For example, NEQ measured at Day 5 in the 24-hour urine collection starts on Day 5 and ends later on Day 6.

At time of Discharge on Day 6, subjects will empty their bladder shortly before 06:29 AM. This will be the last urine portion for the 24-hour urine for the Day 5 dot mark in the Schedule of Events.

7.7.3 Long-Term Bio-banking Storage of Blood or Urine

If a subject gives consent for sample bio-banking for BoExp/risk markers, additional samples of urine (from the 24-hour urine collection) and serum/plasma (20 ml of blood total) will be collected.

- Samples from the 24-hour urine will be collected from the urine collections that started on Day 0 and on Day 5, respectively.
- Serum/plasma will be collected on Day 0 and Day 6.

These samples are intended for possible later analysis of additional BoExp/risk markers. No genetic or transcriptogenomics testing will be performed on these samples.

Confidentiality statement: Data and information contained in this document are considered to constitute trade secrets and confidential commercial information, and the legal protections provided to such trade secrets and confidential information are hereby claimed under the applicable provisions of applicable law. No part of this document may be publicly disclosed without the written consent of Philip Morris Products S.A.

If a subject gives consent for sample bio-banking of whole blood for transcriptomics, a total of 10 ml of blood will be collected to that purpose at Day 0 and Day 6.

The samples intended for sample bio-banking will be kept frozen according to the SHM, separate from the other samples collected, and will be shipped to a central storage facility. After the final CSR is signed, samples of plasma/serum will be stored for a maximum of 5 years and samples of urine will be stored for a maximum of 2 years. The blood bio-banking for transcriptomics will be stored for a maximum of 5 years.

The facility at which the samples are stored will follow their procedures for destruction of banked samples if a subject withdraws their consent for sample bio-banking.

7.8 Other Study Procedures

7.8.1 Human Smoking Topography Assessment

Human smoking topography involves the measurement of each smoker's unique way of smoking CCs or using THS Tobacco Sticks using the HST SODIM[®] device. The HST SODIM[®] device, model SPA/M (SODIM[®] Instrumentation, Fleury les Aubrais, France) is a device which is used to measure smoking topography (see Appendix 4). It consists of a special sample holder (containing a constriction in the middle) which is placed between the subject's mouth and the filter of the CC or THS Tobacco Stick being smoked/used. The sample holder is connected by 2 narrow tubes to a portable data logger/recording system (see Appendix 4 for a description of the device). Any malfunction of the HST SODIM[®] portable device will be documented in appropriate log.

At Day 0, the HST SODIM[®] device has to be used for all CC smoked for all subjects. On Day 1 and Day 4 of the confinement period, the HST SODIM[®] device has to be used for every product use for all subjects in the CC and THS 2.2 arms.

Smoking topography with the HST SODIM[®] device will not be recorded for subjects smoking CC that are incompatible with the HST SODIM[®] device (e.g., slim CC).

For each subject, one HST SODIM[®] device will be assigned at Day -1, which will be used by that subject on all HST assessment days (in the case of malfunction, the device will be exchanged). HST SODIM[®] devices will be assigned to all subjects smoking non slim CCs at each cohort but not more than 40 subjects at each cohort.

From Day 1, for subjects in the SA arm, no HST assessments will be performed.

The Sponsor will provide training on the use of the HST SODIM[®] device to the study site staff. The study site staff will, in turn, provide training to the subjects. All HST SODIM[®] devices will be returned to the Sponsor after completion of the study.

7.8.1.1 Human Smoking Topography Parameters:

The HST SODIM[®] device measures and records the flow and other per-puff parameters listed in Table 4 below. From the per-puff parameters (Table 4), the per-cigarette parameters shown in Table 5 will be derived (representing average values or totals per cigarette).

Prior to calculation of the per-cigarette parameters, the Sponsor's HST group will validate the data and discard any invalid data. Only valid data for the per-cigarette parameters will be part of the study database and will be analyzed.

Table 4. Human Smoking Topography - Per-Puff Parameters

| Description | Variable | Unit |
|------------------------------|----------|-----------|
| Puff number | Ni | |
| Puff volume | Vi | ml |
| Puff duration | Di | s |
| Average flow [Vi/Di] | Qmi | ml/s |
| Peak flow | Qci | ml/s |
| Inter puff interval | Ii | s |
| Sum of Ii and Di | DFi | s |
| Work [INT Pmi*FinalFlow*dt] | Wi | mJ |
| Average pressure drop | Pmi | mmWG |
| Peak pressure drop | Pci | mmWG |
| Average resistance [Pmi/Qmi] | Rmi | mmWG/ml/s |
| Peak resistance [Pci/Qci] | Rci | mmWG/ml/s |

Table 5. Human Smoking Topography - Per-Cigarette Parameters

| Description | Variable | Formula | Unit |
|-----------------------|----------|---------------------------------|------|
| Total number of puffs | NPC | $\sum Ni$ | |
| Total puff volume | TVOL | $\sum Vi$ | ml |
| Average puff volume | AvgVi | $\sum Vi / NPC, i=1 \dots NPC$ | ml |
| Average puff duration | AvgDi | $\sum Di / NPC, i=1 \dots NPC$ | s |
| Total puff duration | TDi | $\sum Di$ | s |
| Average flow | AvgQmi | $\sum Qmi / NPC, i=1 \dots NPC$ | ml/s |
| Peak flow | AvgQci | $\sum Qci / NPC, i=1 \dots NPC$ | ml/s |

Confidentiality statement: Data and information contained in this document are considered to constitute trade secrets and confidential commercial information, and the legal protections provided to such trade secrets and confidential information are hereby claimed under the applicable provisions of applicable law. No part of this document may be publicly disclosed without the written consent of Philip Morris Products S.A.

| Description | Variable | Formula | Unit |
|-----------------------------|------------------|------------------------------------|------|
| Total inter puff interval | Tli | $\sum I_i$ | s |
| Average inter puff interval | AvgIi | $\sum Q_{ci} / NPC, i=1 \dots NPC$ | s |
| Total smoking duration | TDFi | $\sum DF_i$ | s |
| Total Work | TWi | $\sum W_i$ | mJ |
| Average Work | AvgWi | $\sum W_i / NPC, i=1 \dots NPC$ | mJ |
| Average pressure drop | AvgPmi | $\sum P_{mi} / NPC, i=1 \dots NPC$ | mmWg |
| Average Peak pressure drop | AvgPci | $\sum P_{ci} / NPC, i=1 \dots NPC$ | mmWg |
| Smoking Intensity | SMINT | TVOL/TDFi | ml/s |
| Puffing Time Index | PTI | $(100*TD_i)/TDF_i$ | % |
| Puff Frequency | PF _{eq} | $NPC/(TDF_i/60)$ | |

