**Table 8: HST- Per-Puff Parameters**

Description	Variable	Unit
Puff number	Ni	
Puff volume	Vi	mL
Puff duration	Di	s
Average flow [Vi/Di]	Qmi	mL/s
Peak flow	Qci	mL/s
Inter puff interval	Ii	s
Sum of Ii and Di	DFi	s
Work [INT Pmi*FinalFlow*dt]	Wi	mJ
Average pressure drop	Pmi	mmWG
Peak pressure drop	Pci	mmWG
Average resistance [Pmi/Qmi]	Rmi	mmWG/mL/s
Peak resistance [Pci/Qci]	Rci	mmWG/mL/s

Table 9: HST - Per-Cigarette Parameters

Description	Variable	Formula	Unit
Total number of puffs	NPC	$\sum Ni$	
Total puff volume	TVOL	$\sum Vi$	mL
Average puff volume	AvgVi	$\sum Vi / NPC, i=1 \dots NPC$	mL
Average puff duration	AvgDi	$\sum Di / NPC, i=1 \dots NPC$	s
Total puff duration	TDi	$\sum Di$	s
Average flow	AvgQmi	$\sum Qmi / NPC, i=1 \dots NPC$	mL/s
Average Peak flow	AvgQci	$\sum Qci / NPC, i=1 \dots NPC$	mL/s
Total inter puff interval	Tli	$\sum Ii$	s
Average inter puff interval	Avgli	$\sum Qci / NPC, i=1 \dots NPC$	s
Total smoking duration	TDFi	$\sum DFi$	s
Total Work	TWi	$\sum Wi$	mJ
Average Work	AvgWi	$\sum Wi / NPC, i=1 \dots NPC$	mJ
Average pressure drop	AvgPmi	$\sum Pmi / NPC, i=1 \dots NPC$	mmWg
Average Peak pressure drop	AvgPci	$\sum Pci / NPC, i=1 \dots NPC$	mmWg
Smoking Intensity	SMINT	$TVOL/TDFi$	mL/s
Puffing Time Index	PTI	$(100 * TDi) / TDFi$	%
Puff Frequency	PFeq	$NPC / (TDFi / 60)$	puffs/min

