12.6.3.2 Human Smoking Topography Parameters

The HST assessments will take place on Day 0, Day 1 and Day 4 in the THS 2.2 and CC arms only, if CC are compatible with the HST SODIM® device.

The per puff parameters are shown in **Table 8** and the per cigarette parameters are shown in **Table 9**.

The per-cigarette parameters derived from the HST assessments will be summarized along with their changes from baseline. The per-puff and per-cigarette parameters will be listed. In addition the product mean and 95% CI per cigarette parameters will be presented graphically.

The per-cigarette parameters will be analyzed on Days 1 and 4 separately using an ANCOVA model on the log-transformed HST parameter with terms for log-transformed baseline score, sex, average daily CC consumption over the last 4 weeks as reported during screening, product. No adjustment will be made for multiple comparisons.

The SAS code will be the same as described in Section **12.6.1.1 “Primary Biomarkers of Exposure in 24 hour collection”**.

LS means for each product along with the ratio (THS 2.2 : CC) and 95% CI will be presented in the tables.

All figures, summaries and analyses will be performed on the FAS.

The data will be presented in the below outputs, the TFL number refers to the TFL number in the accompanying TFL shell document:

TFL number	Title
FIGURES	
15.1.2.39	HST per Cigarette Parameters Arithmetic Mean and 95% CI – FAS
TABLES	
15.2.4.59	Descriptive Statistics of HST Parameters per Cigarette – FAS
15.2.4.60	Analysis of HST per Cigarette – FAS
LISTINGS	
15.3.7.1	Listing of HST Assessments

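### Protocol Table 5 and SAP Table 9 define average inter puff interval with the peak-flow formula, so this one exploratory topography endpoint is wrong as written

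*Protocol*

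**What the plan says.** Protocol Section 7.8.1 lists the quantities recorded for each puff (Table 4) and the per-cigarette quantities computed from them (Table 5): "From the per-puff parameters (Table 4), the per-cigarette parameters shown in Table 5 will be derived". The row at issue in Table 5 reads "Average inter puff interval | AvgIi | $\sum Q_{ci} / NPC, i=1 \dots NPC$ | s".

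SAP Section 7.4 carries the same pair of tables as Tables 8 and 9, with the same formula and the same unit (s) for this row. SAP Section 5.3 lists "Average inter puff interval" as an exploratory endpoint, separately from average peak flow.

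SAP Section 12.6.3.2 points to Table 9 for the per-cigarette parameters and states: "The per-cigarette parameters will be analyzed on Days 1 and 4 separately using an ANCOVA model on the log-transformed HST parameter". The model adjusts for log baseline, sex and cigarette consumption, and the results are given as a THS 2.2:CC ratio with a 95% CI.

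Neither the list of changes in SAP Section 9 nor the revision history in SAP Section 3.1 mentions a correction.

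**The concern.** The row is labelled as an interval, has an interval variable name (AvgIi) and carries an interval unit, but its formula averages peak flow. Smoking pattern is a stated exploratory objective, and spacing between puffs is part of it. If the derivation follows the table, the plan reports one quantity twice under two names and the average interval is never computed. The seconds label would hide this, because a value in the tens looks plausible for either quantity.

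**Working it through.** The plan gives no numerical value for this parameter, so there is no figure to reproduce. The check is of algebra and units, followed by an illustration on assumed values.

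**Inputs (Protocol Tables 4 and 5; SAP Tables 8 and 9 agree)**

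- Peak flow per puff: "Peak flow | Qci | ml/s"
- Interval per puff: "Inter puff interval | Ii | s"
- Puff duration Di, in s, and DFi, defined per puff as the sum of Ii and Di
- Per-cigarette peak flow: "Peak flow | AvgQci | $\sum Qci / NPC, i=1 \dots NPC$ | ml/s"
- Per-cigarette total interval: "Total inter puff interval | Tli | $\sum I_i$ | s"
- Total smoking duration: TDFi = sum(DFi)

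**Check 1, duplication.** AvgQci = sum(Qci)/NPC, and AvgIi as printed = sum(Qci)/NPC. The difference is zero for every product use, whatever the data and however NPC is defined. The log values, log baselines, model fits, ratios and CIs on Days 1 and 4 would therefore also coincide.

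**Check 2, units.** A sum of ml/s divided by a count is in ml/s. The table says s.

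**Check 3, neighbouring rows.** The row directly above sums Ii. The other simple-average rows (volume, duration, average flow, peak flow, work, average and peak pressure drop) each average the variable in their own name. Only this row does not.

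**Check 4, internal identity.** Since DFi = Ii + Di, summing over puffs and dividing by NPC gives AvgIi + AvgDi = TDFi/NPC.

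**Illustration (assumed values, one cigarette, 10 puffs)**

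- Qci (ml/s): 38, 42, 40, 36, 44, 39, 41, 37, 43, 40; sum 400
- Ii (s): 22, 18, 25, 20, 30, 24, 19, 27, 21, 0; sum 206
- Di (s): 1.6, 1.8, 1.7, 1.5, 1.9, 1.6, 1.7, 1.5, 1.8, 1.7; sum 16.8
- AvgIi as printed: 400/10 = 40.0, equal to AvgQci = 400/10 = 40.0
- AvgIi with Ii: 206/10 = 20.6 s
- TDFi/NPC: (206 + 16.8)/10 = 22.28 s; AvgDi: 16.8/10 = 1.68 s
- Identity as printed: 40.0 + 1.68 = 41.68, which is not 22.28
- Identity with Ii: 20.6 + 1.68 = 22.28, which holds
- Dividing instead by the nine gaps between puffs: 206/9 = 22.9 s; this is a separate denominator question, and that choice would not satisfy the identity

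**The case against.** The strongest reply is that this is a copied cell with an obvious intent: label, variable name, unit and the row above all point to Ii. SAP Section 7.4 adds that the topography data pass through analysis software, whose formula is not shown and may well be right. That stands, and it makes the harm conditional. It does not clear the text. Table 9 is the SAP's only derivation for this endpoint, and the protocol says the parameters in its Table 5 are the ones to be derived. If the software uses Ii, the output departs from the SAP; if it follows the SAP, the output is wrong. A text-extraction fault is unlikely, because two separate documents carry the same formula, and the SAP had edited other cells of the table (it relabelled peak flow as an average and added a unit for puff frequency).

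Stronger readings are tempting but not supported:

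- A reader might infer that nothing would be learned about puff spacing. Total inter puff interval, total smoking duration, puffing time index and puff frequency are in the same tables and the same analysis, and do not use the faulty row. The per-puff data are listed too, so the average can be recovered.
- A reader might infer that every cigarette and stick in the study is affected. Recording is limited to Days 0, 1 and 4, to device-compatible products, to no more than 40 subjects per cohort, and to data that pass validation or processing. The SA arm is not recorded from Day 1.
- A reader might infer that the reported effect would point the wrong way. The documents give no topography values. With assumed peak flows of 40 (CC) and 50 (THS 2.2) ml/s, the printed formula gives a ratio of 50/40 = 1.25. Assumed intervals of 25 and 18 s give a true ratio of 18/25 = 0.72, a reversal; swapping those intervals gives 25/18 = 1.39, the same direction. A reversal is possible, and no more can be said.

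**Conclusion.** The formula is wrong as written in both documents; this follows from the tables alone and needs no assumed data. Its reach is one of 17 per-cigarette parameters under an exploratory objective, over valid device-recorded uses. If it is derived literally, that parameter and its Day 1 and Day 4 ratios and CIs repeat average peak flow under a seconds label. The primary biomarkers, success criterion, sample size and safety results are untouched.

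The conclusion that a result would be wrong rests on one assumption the documents do not settle: that the software or derivation program follows the printed formula. The size of any numerical error cannot be stated from the documents; 40.0 against 20.6 is an illustration only. The point is still worth acting on, because a listed and analysed endpoint should have a correct specification and the remedy costs almost nothing.

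**What to change.** In the AvgIi row of Protocol Table 5 and SAP Table 9, replace Qci with Ii, so that AvgIi = sum(Ii)/NPC in seconds. This matches the other average rows and the relation DFi = Ii + Di. Keep sum(Qci)/NPC for average peak flow only. Confirm that the analysis software or derivation program uses Ii; one check is that AvgIi + AvgDi equals TDFi/NPC on a few recorded uses.

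As a separate query, the sponsor should confirm whether the last puff of a product use has a recorded interval, and so whether the denominator should be the number of recorded intervals instead of NPC. The documents do not say, and the correction above does not depend on the answer.

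Cost: one symbol in each of two tables and a short program check. No new data and no change to any other analysis.
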